## **Data Management**

We will conduct a training session and mock study visit before initiating enrollment to ensure uniformity in procedures and data collection at both sites. The Boston and Birmingham teams will interact directly with study subjects, coordinate follow-up, and monitor AdEs. Study staff on all 3 teams will communicate daily by secure VA email and participate in conference calls every other week to ensure valid, accurate, and consistent methods in data collection. All data will be coded with a unique study identification number. Outcomes data will be collected by paper and pencil and stored in study binders, locked in study staff offices. Databases located on an internal computer drive within the VA firewalls and accessible to both VA sites will be used for data storage. Data will be entered in Access databases, cleaned, and exported to SAS for statistical analyses. University of Michigan staff will manage the step-count data associated only with each subject's study ID. All computers and data files will be password-protected and backed up at regular intervals. All data will be processed and analyzed in aggregate.

## **Information Security**

Participants are enrolled at VABoston and VABirmingham. The study website is maintained by staff at the University of Michigan who have no direct contact with any study participants.

At both recruiting sites, study records and blood samples are identified only by an assigned unique study ID. One master list links the study ID with the participant's name and other identifiable information. This master list is located on a secured network behind the VA firewalls.

At VABoston and VABirmingham, study data will be collected by paper and pencil. The paper documents are stored in locked file cabinets in locked offices. These data will be entered in duplicate by study staff into Access databases, which are located on a shared drive on the secured network behind the firewalls of VABoston. These databases are located behind the VABoston firewalls and will be accessible only via VA secured and password protected desktops in locked study staff offices. We will request permission for access to the shared drive by [name] and his study staff at VABirmingham. This will be necessary to ensure study uniformity and that data from VABirmingham will be entered into the study databases for aggregate analyses. All study data in the databases will be identified only by the participant's unique study ID.

All blood samples will be identified only by the participant's unique study ID. Samples are overnight shipped to MAVERIC from VABoston and VABirmingham using FedEx courier. Samples are processed and stored at MAVERIC. Blood samples will be stored in freezers located behind locked doors at VA Boston for an indefinite period of time. Only approved VA employees have access to the areas where blood samples are kept.

The study uses a website created and maintained by [name] and her staff at the University of Michigan. They have no direct contact with any study participants. After the account is created, participants access the website using their unique username and password. Participants will upload step-count data to the website over the Internet. These data are stored on a study server on a secure network behind the firewalls of the University of Michigan. Per policies of the University of Michigan, the website is secured, the study server is located on a secured network, and data are backed up at regular intervals. The data stored on the study server are: unique study ID, username and password, and step count numbers. No protected health information (PHI) will be stored on the study server. The UMich server does not track IP addresses. A Data Use Agreement between the University of Michigan and VABoston and VABirmingham will be executed before the study starts.

In addition, test results from this research study as well as hospitalization records, laboratory test results, and radiology reports from care provided outside of the VA may be disclosed to [name] and his research staff at the VA Birmingham, and to the members of the Data and Safety Monitoring Board who oversee this study. This information would be associated only with the participant's unique study ID.

Removal of access to research study data will be accomplished for study personnel when they are no longer part of the research team.

In accordance with VA Policy, procedures are in place for reporting incidents. All incidents will be reported immediately to the PI, the VA Boston Information Security Officers and Privacy Officers, and to the VA Boston Institutional Review Board.

### **Statistics (power analysis)**

Prior to analyzing the outcomes, we will summarize and compare baseline demographic and clinical variables by treatment group. Any unbalanced characteristics occurring despite randomization will be assessed as potential confounders in multivariate analyses. Analyses will be performed with the SAS statistical software package (9.3, SAS Institute; Cary, NC).

**Primary Aim:** To determine the efficacy of the WEB intervention to increase 6MWT distance.

We focus on 6MWT distance at 6 months since we predict that the greatest difference in 6MWT distance between study arms will occur at month 6, at the end of the interventional phase. We have revised our statistical analysis plan to use 2-way factor analysis or analysis of variance (ANOVA). This approach will assess the effect of intervention versus control on 6MWT distance, using absolute measures of 6MWT distance at baseline and 6 months. Two-way ANOVA will allow us to assess the effect of treatment (intervention versus control), and additionally allow us to assess the interaction between treatment and time (treatment-time) on 6MWT distance. We will use a mixed model (PROC MIXED in SAS) to perform the 2-way ANOVA given its flexibility of modeling the variances and covariances, its robustness in accounting for correlated data (repeated measures data), and its flexibility in handling missing data. Models will have 6MWT distance as the dependent variable, and treatment, time, and treatment-time as independent variables. In this approach, models will also include study site and any unbalanced baseline characteristics as covariates. Primary analyses to determine the effect of WEB on 6MWT distance will use the intention-to-treat approach to include as many randomized subjects as possible in the analyses. Subjects will be considered to be in his/her randomly assigned arm no matter how much he/she participated in it. As a sensitivity analysis, however, we will examine 6MWT distance on a per-protocol basis, where noncompliant subjects ( $\geq 30\%$  of days with no exercise performed on logs) in each treatment arm will be excluded from the analysis.

**Anticipated Results:** We anticipate that subjects in the intervention group will have significantly higher 6MWT distance than subjects in the control group at 6 months.

**Power Calculation:** This study is powered on our pre-specified primary outcome of 6MWT distance. Our main comparison is 6MWT distance at 6 months between the WEB intervention and control arms. Our power analysis is based on a widely accepted minimum clinically meaningful change in 6MWT distance of 54 meters and the published standard deviation for 6MWT distance of 80-120 meters (90). Our data in a similar Veteran population showed a standard deviation of 102 meters for 6MWT distance. We use a standard deviation of 100 meters in our power calculation. Using the sample size formula for the comparison of the means of 2 independent samples, we calculate that 55 evaluable subjects in each arm at 6 months will allow

[figure not shown]

detection of a difference of at least 54 meters between the WEB and usual care arms with a power of 80% and  $\alpha=0.05$ . We anticipate a maximal drop-out of 40% at 6 months. In order to have 111 evaluable subjects at 6 months, we plan to enroll a total of 185 subjects.

**Secondary Aims:** To estimate the effect of the WEB intervention on (a) HRQL, as measured by the St. George's Respiratory Questionnaire (SGRQ), (b) dyspnea, (c) CRP and IL-6, (d) risk of AEs and COPD-related hospitalizations, (e) engagement in PA as measured by daily step count, (f) body composition and bone mineral density, and (g) pain.

Our statistical analysis plan for the secondary outcomes is similar to that for the primary outcome. We will use 2-way factor analysis or analysis of variance (ANOVA) to assess the effect of intervention versus control on SGRQ-TS, dyspnea score, CRP and IL-6, and daily step count. We will analyze absolute values of the secondary outcomes at baseline and 6 months. Two-way ANOVA will allow us to examine the effect of our intervention, and additionally allow us to assess the interaction between treatment and time (treatment-time) on the secondary outcomes. We will use a mixed model (PROC MIXED in SAS) to perform the 2-way ANOVA. Models will have SGRQ-TS, dyspnea score, CRP and IL-6, or daily step count as the dependent variable, and treatment, time, and treatment-time as independent variables. Models will also include study site and any unbalanced baseline characteristics as covariates.

Total number of AEs and COPD-related hospitalizations will be summed over the 12-month study period. Independence of individual AEs will be assured by considering subjects to have experienced a new AE only if they had been off of oral steroids and antibiotics for at least 14 days following the previous AE (86). Given the count data and expected Poisson distribution of number of AEs and hospitalizations, negative binomial regression models (PROC GENMOD) will be used to calculate risk ratios for AE and COPD-related hospitalizations (86). The

multivariate regression model will include number of AEs (or hospitalizations) as the dependent variable, treatment group as the main predictor, as well as study site, number of AEs (or hospitalizations) in the year prior to enrollment, and any unbalanced baseline characteristics.

**Body Composition by DXA Scan:** Body composition and regional fat analysis will be performed at the baseline study visit and the 12-month study visit using standard software available from the manufacturer. For regional fat measurements, the left and right arm cuts pass through the shoulder joints and as close to the body as possible. The leg cuts separate the hands and forearms from the legs, starting with a diagonal cut through the femoral necks. The midline separates the right and left legs. The images obtained from one of our subjects demonstrate the standard cuts that define the arms, legs, and trunk (see figure to the left). These data can be also be used to calculate a waist-hip ratio (i.e., ratio of

central fat to hip fat) in a standardized fashion using the same landmarks as illustrated by the regions defined on the soft-tissue image. The DXA software can be used to define standard waist and hip regions that will allow comparability of these measurements throughout the study. The lower boundary of the central or waist region, which is also referred to as the android region (A, see figure), is the cut through the pelvis at the level of the iliac crests. The upper boundary of the android region extends upwards to 20% of the distance between the pelvis and the top of the shoulders and the lateral boundaries are the arm cuts. The upper boundary of the gynoid region of interest (G, see figure) is the region below the pelvis cut that extends downward from 1.5 times the height of the android region. Lateral boundaries of the gynoid region are the outer leg cuts.

The waist to hip fat ratio, or android to gynoid ratio, is the percent fat in the android region divided by the percent fat in the gynoid region. Percent fat mass in each region is reported as the total of the percent fat in the right and left sides. The precision of regional fat measurements is +/-1%.

Subjects will be asked to complete a body composition measurement using the Omron Fat Loss Monitor (model HBF-306CN) in order to compare body fat measurements with the DXA. Since DXA is the gold standard, the Omron Fat Loss Monitor is being examined as a cost-effective and less invasive alternative method to measure body fat composition. The monitor has been approved for use in the general population except in individuals who are pregnant or who have implanted medical devices such as pacemakers or defibrillators; we will therefore exclude any subject who is pregnant or who has a pacemaker or defibrillator to minimize any potential risks.

**Anticipated Results:** We anticipate that subjects in the intervention group will have better HRQL, less dyspnea, lower CRP and IL-6 levels, higher daily step count, lower adiposity, higher bone mineral density and lower risk of AEs and COPD-related hospitalizations compared to subjects in the control group at 6 months.

**Power Calculations:** A sample size of 111 evaluable subjects at 6 months determined by the primary outcome of 6MWT distance will also allow detection of significant differences in the secondary outcomes. Using the sample size formula for the comparison of the means of 2 independent samples, we can detect an effect size of 0.55 SD units with 80% power and  $\alpha=0.05$ . Using the SD's obtained from our cross-sectional observational study, we can detect a change of at least 10 units in SGRQ-TS, 1.8 mg/L in CRP level, and 0.59 pg/mL in IL-6 level. In addition, as an estimate for anticipated differences between arms, we examined the mean 6MWT distance, SGRQ-TS, CRP, and IL-6 levels in those who walked above and in those who walked below the median daily step count in our observational data. We observed a difference of 1.27 pg/mL in IL-6 in those who walked above and in those who walked below the median daily step count, values greater than our detectable difference suggesting sufficient power. We found a difference of 7 units in SGRQ-TS and 0.96 mg/L in CRP. While these preliminary observed estimates of difference in SGRQ-TS and CRP are slightly smaller than our calculated detectable estimates, we anticipate there will be sufficient power to detect differences in these secondary outcomes when the analyzed groups are differentiated by the WEB intervention, since our power calculations based on groups dichotomized at the median step count are conservative. In calculating power for detecting differences in risk of AEs, we expect to observe 106 AEs in the 111 subjects completing a 12-month follow-up period based on our preliminary data. Given this rate and using the POISS\_SS macro of E. Bergstralh (a Poisson power calculator), we will be able to detect a rate ratio of at least 1.70 with 80% power and 1.85 with 90% power. Again, to estimate anticipated observed differences between treatment arms, we examined the number of AEs in those who walked above and in those who walked below the median daily step count in our observational data. One hundred thirty-six AEs were observed in those who walked below the median daily step count and 76 AEs were observed in those who walked above the median daily step count, an observed rate ratio of 1.79, indicating adequate power.

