## **Baseline Visit**

### **D.3. Baseline Visit**

When interested subjects are scheduled for the baseline clinic visit, they will be mailed a medical clearance form which will have been signed by their healthcare provider. The signed clearance form must be faxed or submitted to study staff prior to randomization and assignment to a study arm. At the baseline study visit, we will review the participant's medical history and obtain information about demographics, cigarette use, and prior participation in pulmonary rehabilitation. Comorbidities of coronary artery disease, congestive heart failure, diabetes, and other diagnoses that affect the lower limbs (osteoarthritis or degenerative joint disease, hip or knee replacements, rheumatoid arthritis, chronic low back pain, lumbar spine disease, peripheral vascular disease, or peripheral neuropathy) will be noted. We will record medication use and current use of supplemental oxygen. We will also assess history of AEs and related medication use in the previous 12 months since prior AE strongly predicts future AEs (83). Weight and height will be measured for the calculation of body mass index (BMI). Baseline data will characterize the cohort and allow analysis of potential confounders.

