Based on our previous work, medical problems and temporary suspension from the exercise program will be the most common reason for missing outcomes data in both arms. We have designed the testing windows to minimize missing data. At months 3 and 6, testing will be allowed within a window of  $\pm 2$  weeks. At months 9 and 12, testing will be allowed within a window of  $\pm 1$  month, making the total participation time up to 13 months from the baseline in-clinic study visit (C00). Despite our efforts at follow-up, some missing data are expected with multiple testing visits. We will collect the reasons for missing data such as death, COPD exacerbation, medical reasons, or non-medical reasons. We will compare the rate of losses to follow-up at 3, 6, 9, and 12 months among the two arms using the chi-square test of association. We will assess whether any baseline characteristics such as age, FEV1 % predicted, or 6MWT distance, are associated with losses to follow-up using chi-square tests for categorical baseline data and analysis of variance for continuous baseline data. If baseline variables and treatment group are found to be associated with loss to follow-up, then the analysis models will be modified to include the differing baseline variables as covariates to provide unbiased estimates of intervention effects. For subjects who discontinue the study early due to worsening of COPD or due to death, missing outcome data will be imputed using the least favorable data observed prior to discontinuation. Missing data for subjects who miss a visit not related to worsening of COPD will be imputed using last observed data. We will also perform sensitivity analyses using the complete case method, excluding those with no observed outcome at 6 months.

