As outlined in our Conceptual Model, we will also explore whether increases in PA (6MWT distance and daily step counts) result in decreases in levels of systemic inflammation and risk of AEs, regardless of treatment arm. Models, adjusting for baseline 6MWT distance or step counts, will examine whether increases in PA independently predict decreases in inflammatory biomarkers and decreased risk of AEs and COPD-related hospitalizations. We will use linear regression models with change in 6MWT distance as the independent variable, and change in IL-6 and CRP as dependent variables. A multivariate regression analysis (PROC GENMOD) will be conducted with number of AEs (or COPD-related hospitalizations) as the dependent variable, and change in daily step count and baseline daily step count as independent variables. Models will account for potential confounders such as study site, season of enrollment, age, gender, comorbid medical conditions, FEV1 % predicted, BMI, and history of prior AEs. We believe we will show that increases in 6MWT and daily step count, regardless of treatment arm, independently predict decreases in CRP and IL-6, and decreases in the risk of AEs and COPD-related hospitalizations. These exploratory models have the potential to provide significant insight into the mechanisms of the beneficial impact of walking and PA on systemic inflammation and COPD-related morbidity. The results of these exploratory analyses will provide estimates for sample size calculations for future research proposals.

(d) Discuss potential problems and limitations of the proposed methods and/or procedures and possible alternative procedures to achieve the specific aims.

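### Apart from site and prior-year events, model covariates are chosen by undefined baseline imbalance instead of from a prespecified prognostic list

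*Combined protocol and SAP*

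**What the plan says.** Under Statistics (power analysis), the plan first sets a general rule: "Prior to analyzing the outcomes, we will summarize and compare baseline demographic and clinical variables by treatment group". It continues: "Any unbalanced characteristics occurring despite randomization will be assessed as potential confounders in multivariate analyses".

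The rule then enters each model family:

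- **Primary model (6MWT at baseline and 6 months):** "In this approach, models will also include study site and any unbalanced baseline characteristics as covariates".
- **Continuous secondary outcomes:** "Models will also include study site and any unbalanced baseline characteristics as covariates".
- **Exacerbations and hospitalizations:** treatment group "as well as study site, number of AEs (or hospitalizations) in the year prior to enrollment, and any unbalanced baseline characteristics".
- **Repeated-measures models under Additional Analyses:** site and unbalanced subject characteristics again.

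No section says what counts as unbalanced, which variables are candidates, or how many may enter. The general rule has unbalanced variables assessed; the model paragraphs have them included. The two are not reconciled.

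The section on attrition and missing data adds a separate data-driven rule. If baseline variables and arm are associated with loss to follow-up, "then the analysis models will be modified to include the differing baseline variables as covariates".

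Elsewhere the plan does select by prognosis. Section D.3 collects prior exacerbations because they predict later ones, and the event model always includes them. The exploratory mechanism models name their covariates: "Models will account for potential confounders such as study site, season of enrollment, age, gender, comorbid medical conditions", with FEV1 % predicted, BMI and prior exacerbations also listed.

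**The concern.** In a randomized trial, baseline differences between arms arise by chance. Selecting covariates by those differences picks variables without regard to whether they predict the outcome. A strong predictor that happens to be balanced is left out, although adjusting for it would still reduce residual variance. An irrelevant variable that happens to differ goes in and costs a little precision.

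Because the term is undefined, two competent analysts could follow the plan and fit different primary models. Section D.3 lists more than 20 baseline measures, so there is ample room for this. Nothing excludes baseline 6MWT from the candidates either. If it were flagged, it would be both a response and a covariate in the two-time-point model.

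At stake are precision and a fixed model for the month-6 between-arm comparison, which the power calculation calls the main comparison, and for the event models, which have no time term.

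**Working it through.** **1. The plan's own figure.** Inputs from the Power Calculation: difference 54 m, SD 100 m, alpha 0.05 (two-sided assumed; sidedness is not stated), 55 per arm.

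- SE = 100 × √(2/55) = 19.07 m.
- 54/19.07 = 2.832.
- Power = Φ(2.832 − 1.96) = 80.8% (80.1% with the t distribution).
- 111/(1 − 0.40) = 185.

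The plan's figures reproduce.

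**2. How often imbalance finds a predictor.** Assumptions not in the documents: 25 independent candidates, three of them predictive (none being baseline 6MWT), flagged at p<0.05.

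- At least one flagged: 1 − 0.95^25 = 72%.
- At least one of the three predictors flagged: 1 − 0.95^3 = 14%.

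**3. Cost of one irrelevant flagged variable.** A variable just significant at 0.05 on 108 df has t = 1.982. Its squared correlation with arm is 1.982²/(1.982² + 108) = 0.035, so the variance rises by 1/(1 − 0.035) = 1.036. Power is Φ(2.832/√1.036 − 1.96) = 79.4%. Two such variables give 78.0%, three 76.4%.

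**4. Month-6 power with the rule and with a fixed list.** With three predictors each correlating 0.25 to 0.35 with the outcome, joint R² = 3 × 0.25² = 0.19 to 3 × 0.35² = 0.37. Ordinary least squares on simulated month-6 data, 55 per arm:

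| Analysis | Power |
|---|---|
| No adjustment | about 80% |
| Variables flagged at p<0.05 | about 78-79% |
| Three predictors always included | 86-93% |

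Approximate check on the last row, ignoring the small loss from estimating three coefficients: Φ(2.832/√(1 − 0.1875) − 1.96) = 88%, and Φ(2.832/√(1 − 0.3675) − 1.96) = 95%.

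**5. Sensitivity to the candidate pool.** With 10 candidates instead of 25, and flags at 0.05 or 0.20, against about 81% unadjusted:

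| Candidates | Power with the rule |
|---|---|
| None prognostic | 78.1-79.9% |
| Total R² 0.3-0.5 | 81.5-85.2% |
| Baseline 6MWT also a candidate | 82.0-90.0% |

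The direction against no adjustment therefore depends on assumptions.

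**6. Type I error.** With a fixed 5% flag and the 25 candidates it is 4.1-4.9%. With 10 prognostic candidates (baseline 6MWT among them in some runs) it is 1.9-4.5%. It is not inflated; if anything the test is conservative.

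**7. The treatment-time contrast.** In one simulated two-time-point data set without missing values, the estimate (0.7095) and SE (0.1430) were identical with and without an unbalanced time-invariant covariate. Such a covariate cancels from within-person change.

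**8. Baseline 6MWT as a covariate when month 6 is the response.** Residual SD is 100√(1 − ρ²). For the change contrast the SD is 100√(2(1 − ρ)). The correlation ρ is assumed:

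| ρ | Month 6, baseline-adjusted | Treatment-time contrast |
|---|---|---|
| 0.5 | 90.5% | 80.8% |
| 0.7 | 97.8% | 95.5% |
| 0.8 | 99.7% | 99.4% |

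**The case against.** The strongest defence is that the plan is less open than the clause suggests. Site is fixed everywhere, and prior-year events are fixed in the event models for a prognostic reason. Baseline 6MWT is already in the primary model as a response. The baseline comparison comes before outcome analysis, and being assessed as a confounder could include checking the link with the outcome. The treatment-time test with complete data, which the imputation rules bring close, does not depend on these covariates. All of this stands and limits the point to the remaining covariates and to the month-6 and event comparisons. It does not supply a definition or a list.

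A reader might infer three stronger things that the documents do not support:

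- **That the rule costs power against no adjustment.** It does so by 1 to 3 points when the candidates are mostly unrelated to the outcome. When they are prognostic, the sign reverses. The baseline measures include several overlapping severity scales, so 3 independent predictors among 25 is an illustration only.
- **That it inflates type I error.** A rate of 7-8% arises only if the best of four analyses (no adjustment, or flags at 0.05, 0.10 and 0.20) is chosen after the outcome p-values are seen. The plan puts the baseline comparison first, so that is misuse and not the stated rule.
- **That no covariate is chosen for prognosis.** The prior-year count plainly is.

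**Conclusion.** The point holds in limited form. Beyond site and, for events, the prior-year count, the plan's confirmatory models take their covariates from undefined observed imbalance. The models stay unfixed until baseline data by arm are seen, and precision is forgone in the month-6 between-arm comparison and the event models.

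Under the illustrative assumptions the month-6 shortfall is roughly 8 to 14 points (about 78-79% against 86-93%). That range rests on the assumed correlations and on a month-6-only model, which approximates the month-6 contrast of the planned mixed model. It is also the gain from three hypothetical predictors. The documents give no correlation of age or FEV1 % predicted with 6MWT, so the gain from the list proposed below cannot be stated. No size was computed for the event models. The treatment-time contrast with complete data is not affected.

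**What to change.** In the Primary Aim, Secondary Aims, exacerbation/hospitalization and Additional Analyses paragraphs, delete the clause on unbalanced baseline characteristics. Before unblinding, fix a short list to be used whatever the observed balance:

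- all models: study site, age and FEV1 % predicted;
- exacerbation and hospitalization models: also the prior-year count, as now;
- baseline value of the outcome: as a covariate only where baseline is not also a response, for example a model with month 6 as the response. In the two-time-point and repeated-measures models it stays a response only.

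Delete or align the general sentence about assessing unbalanced characteristics, and present the baseline table descriptively, without using it to select covariates. A model driven by imbalance may remain as a labelled sensitivity analysis.

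The cost is wording only: every listed variable is already collected.
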